8.4.3.7 Antigen-specific T cells

The presentation and analysis of antigen-specific T cell will be described in a separate Biomarker SAP that will be created by BioNTech.

8.4.3.8 Pharmacodynamic analysis

8.4.3.8.1 Biomarker Analysis

Biomarker investigations in this trial will include pharmacodynamic biomarkers to confirm biological activity of BNT111 as monotherapy and in combination with cemiplimab and predictive biomarkers that may identify patients that can benefit from therapy.

An overview of the biomarker samples that will be collected in this trial is provided in the SoA.

Biomarker assessment summaries for the CSR will focus on:

8.4.3.8.1.1 Occurrence of BNT111 target Tumor-associated Antigen (TAA) expression

Occurrence of BNT111 target TAA expression in tumor tissue at baseline [Positive/Negative] (4 targets: New York esophageal squamous cell carcinoma-1 (NY-ESO-1), tyrosinase, melanoma antigen A3 (MAGE-A3), transmembrane phosphatase with tensin homology (TPTE)).

This TAA expression and the cumulative TAA expression will be summarized using descriptive summary statistics by treatment group for the safety set based on patients with available data. This summary statistics will also be produced at IA2.

8.4.3.8.1.2 Continuous PD-L1 Tumor Proportion Score (TPS)

Continuous PD-L1 TPS at baseline in percentage (central PD-L1 test results). These biomarker data will be summarized using descriptive summary statistics by treatment group for the cells set. This summary statistics will also be produced at IA2.

8.4.3.8.1.3 Categorical PD-L1 Tumor Proportion Score (TPS)

Categorical (Positive/TPS≥1% vs Negative/TPS<1%) PD-L1 expression at baseline (central PD-L1 test results). The biomarker values will be summarized using descriptive summary statistics by treatment group for the set. This summary statistics will also be produced at IA2

Additionally, summary statistics by response ((CR, PR) vs SD vs PD; based on BICR assessed RECIST 1.1) will be produced within treatment group for the color set. At IA2, the above summary statistics will also be produced.

Statistical Analysis Plan (SAP) BNT111-01 Page 43 of 78 Version: Final v7.0 Date: 05Mar2024

BOR, ORR and DCR will be summarized with absolute and relative frequencies (n, %) by categorical PD-L1 expression at baseline within the treatment group. A box plot of PD-L1 expression by Response Status (BICR assessed RECIST 1.1) will be generated by treatment group for set. At IA2, the plot will be produced. PFS and OS will be analyzed by Kaplan-Meier estimates and the corresponding Kaplan-Meier plots will be produced, according to BICR assessed RECIST 1.1.

8.4.3.8.1.4 Peripheral Cytokine Profiles

Peripheral cytokine profiles under treatment over time [absolute values]. The biomarker values at each time-point will be summarized using descriptive summary statistics and shown in boxplots by treatment group for the columns.

8.4.3.8.1.5BRAF Mutations at Baseline

BOR, ORR and DCR will be summarized with absolute and relative frequencies (n, %) by BRAF mutation at baseline (Section 7.3). For BOR, ORR, DCR and PFS, the analyses will be performed according to BICR assessed RECIST 1.1 for the color set. At IA2, the above analyses will be performed.

8.5 Safety analyses

Safety data that will be summarized includes trial treatment exposure, adverse events (AEs), clinical laboratory assessments, vital signs and ECGs. All safety analyses will be based on the Safety set and Add-on Treatment set and will be summarized by treatment group unless otherwise stated.

All safety data will be listed.

See Section 8.1 for data selection using the Safety set and Add-on Treatment set.

8.5.1 Extent of exposure

The following dose exposure variables will be derived and analyzed for each trial treatment: The analyses will be based on patients in the Safety set and will be repeated for the Add-on Treatment set.

- Number of cycles received. For BNT111, a cycle is considered if at least 1 injection within the cycle is taken.
- Number of BNT111 injections and cemiplimab infusions
- (Actual) Trial Treatment Duration (weeks) for the summary using the Safety set, is defined as follows: (Date of last administration - Date of first administration + Planned Duration) / 7, where the Planned Duration (days) is defined as the planned time between two consecutive administrations. Planned duration for BNT111 is one week for the 2 first cycles, followed by once every 3 weeks; planned duration for cemiplimab is 3 weeks. Actual treatment duration is calculated for each treatment separately.
- (Actual) add-on Treatment Duration (weeks) for the summary using the add-on treatment Set is defined as follows: (Date of last administration of add-on - Date of first

Page 44 of 78 Version: Final v7.0 Date: 05Mar2024

administration of add-on + Planned Duration) / 7, where the Planned Duration (days) is defined as the planned time between two consecutive administrations. Planned duration for BNT111 is one week for the 2 first cycles, followed by once every 3 weeks; planned duration for cemiplimab is 3 weeks. Actual add-on treatment duration is calculated for each add-on treatment separately.

- Planned treatment duration (weeks) defined as (scheduled study day of last administration - scheduled study day of first administration + Planned Duration) / 7.
 Planned duration is as above.
 - ➤ The scheduled study day of last administration is the study day at which the last administration should be given according to the protocol schedule. For example, if the schedule is once every 3 weeks and the patients received 2 administrations (at C1D1 and C3D1), the scheduled study day of last administration would be day 43.
- (Actual) Treatment duration (weeks), of the randomized treatment, for the summary using the Add-on Treatment set, the duration of randomized treatment from first dose of Add-on treatment is defined as follows: (Date of last administration Date of first administration received after enrollment into Add-on treatment + Planned Duration) / 7, where the Planned Duration (days) is defined as the planned time between two consecutive administrations. Planned duration for BNT111 is one week for the 2 first cycles, followed by once every 3 weeks; planned duration for cemiplimab is 3 weeks. Actual treatment duration is calculated for each treatment separately.
- (Actual) Cumulative Dose defined as sum of all administered doses, separately, for each trial treatment. BNT111 (µg) and cemiplimab (mg).
- Planned cumulative dose defined as sum of all planned doses, separately, for each trial treatment. BNT111 (µg) and cemiplimab (mg). This is calculated as planned cumulative dose across all the cycles.
- Dose Intensity (DI) is defined as Cumulative Dose for that trial treatment (unit for that trial treatment) / (Actual) Treatment Duration (weeks) for that trial treatment.
- Relative Dose Intensity (RDI) defined as follows:

RDI (%) =
$$\frac{\text{Actual Dose Intensity } \left(\frac{\mu g}{\text{week}}\right)}{\text{Planned Dose Intensity } \left(\frac{\mu g}{\text{week}}\right)} \times 100 = \text{DI x TI x 100,}$$

where,

(Actual) Dose Intensity
$$\left(\frac{\mu g}{\text{week}}\right) = \frac{\text{(Actual) Cumulative Dose (}\mu g\text{)}}{\text{(Actual) Treatment Duration (weeks)}}$$

Statistical Analysis Plan (SAP) BNT111-01 Page 45 of 78 Version: Final v7.0 Date: 05Mar2024

Planned Dose Intensity
$$\left(\frac{\mu g}{\text{week}}\right) = \frac{\text{Planned Cumulative Dose }(\mu g)}{\text{Planned Treatment Duration (weeks)}}$$

Dose Index (DI) = $\frac{\text{Total Administered Dose }(\mu g)}{\text{Total Planned Dose }(\mu g)}$

Time Index (TI) = $\frac{\text{Planned Treatment Duration (weeks)}}{\text{Actual Treatment Duration (weeks)}}$

The units in the derivations above are for BNT111. For cemiplimab mg would be used.

The following variables will be presented with summary statistics by treatment group (as relevant for that treatment group) for the Safety set and the Add-on Treatment set:

- Number of cycles received (categorical, cycles 1,2,3,4,5,6,7,8,9,10-12,13-15,16-18,19-24,25-30, >30). For BNT111, a cycle is considered if at least 1 injection within the cycle is taken.
- Number of BNT111 injections and cemiplimab infusions (descriptive statistics)
- Number of BNT111 injections (categorical, ≤6 injection, 7-12 injections, 13-18 injections,
 >18 injections)
- Number of cemiplimab infusions (categorical, 1, 2, up to 9 then 10-12, 13-15 and so on)
- · Duration of treatment
- · Cumulative dose
- Dose intensity
- Relative dose intensity

Additionally, the relative dose intensity will be presented categorically (i.e., number and percentage of patients with relative dose intensity of <60%, 60-80%, ≥80. Moreover, the number and percentage of patients with any dose delay, dose modification, at least 1 dose modification and at least 2 dose modification any dose interruption and any dose prolonged will be presented by treatment group. This summary will also be repeated for mITT set.

8.5.2 Adverse events

Adverse events (AEs) will be coded using Medical Dictionary for Regulatory Activities (MedDRA®) coding system version 23.1 or later to get a System Organ Class (SOC) and Preferred Term (PT) for each AE and graded for severity using NCI CTCAE v5.0. In case a patient has an AE with missing relationship status, the event will be assumed to be related and associated with the treatment received in the summaries (will be listed as collected in the listings). No imputation for missing NCI-CTC grades will be performed.

TEAEs for randomized treatment

A treatment-emergent AE (TEAE) is defined as any AE with an onset date on or after the first administration of trial treatment (if the AE was absent before the first administration of

Statistical Analysis Plan (SAP) BNT111-01

Page 46 of 78 Version: Final v7.0 Date: 05Mar2024

trial treatment) or worsened after the first administration of trial treatment (if the AE was present before the first administration of trial treatment). AEs with an onset date more than 90 days after the last administration of trial treatment will be considered as treatment emergent only if assessed as related to trial treatment by the investigator, prior to start of Add-on treatment, if applicable, whichever comes first.

An AE will be considered TE for the randomized treatment if it started within 90 days of last dose of randomized treatment or until start of add-on treatment whichever comes first.

Add-on TEAEs

Treatment-emergent for add-on treatment is defined as any AE with an onset date on or after the first administration of add-on treatment (if the AE was absent before the first administration of add-on treatment) or worsened after the first administration of the add-on treatment (if the AE was present before the first administration of add-on treatment). AEs with an onset date more than 90 days after the last administration of add-on treatment will be considered as TE only if assessed as related to add-on treatment by the investigator.

TEAEs for both randomized and add-on treatment

Treatment emergent for both randomized & add-on treatment is defined as any AE with an onset date on or after the first administration of randomized treatment / add-on treatment (if the AE was absent before the first administration of randomized treatment / add-on treatment) or worsened after the first administration of randomized treatment / add-on treatment (if the AE was present before the first administration of randomized treatment / add-on treatment). AEs with an onset date more than 90 days after the last administration of randomized/add-on treatment will be considered as TE only if assessed as related to randomized/add-on treatment by the investigator. If an AE is treatment emergent for the randomized treatment and worsens in intensity during the Add-on treatment, the AE will appear only once in the summary.

TEAEs for randomized, add-on TEAEs and TEAEs for randomized and add-on treatment will be summarized by treatment group and overall for patients in the Safety analysis set and the Add-on Treatment set.

Adverse Events of Special Interest (AESI)

- Grade ≥2 infusion-related reactions related to cemiplimab are considered AESIs.
- Grade ≥3 irAEs (immune-related AEs) related to cemiplimab are considered AESIs.

Overall summary of adverse events (AE)

The number and percentage of patients reporting at least one AE will be summarized for each of the following AE types (summary applies to both BNT111 and cemiplimab unless otherwise specified):

- Any AE
- TEAE
- Related TEAE (BNT111, cemiplimab and both)

Page 47 of 78 Version: Final v7.0 Date: 05Mar2024

- Grade ≥3 TEAE
- Related grade ≥3 TEAE (BNT111, cemiplimab and both)
- Any TESAE
- Related TESAE (BNT111, cemiplimab and both)
- TESAE leading to death
- Related TESAE leading to death (BNT111, cemiplimab and both)
- Any AESI
- Grade≥ 2 infusion-related reactions (IRRs) related to cemiplimab
- Grade≥ 3 irAEs (immune-related AEs) related to cemiplimab
- TEAEs leading to dose reduction (BNT111)
- TEAEs leading to dose interruption (BNT111, cemiplimab and both)
- TEAEs leading to permanent discontinuation of treatment
- Related TEAEs leading to dose reduction (BNT111)
- Related TEAEs leading to dose interruption (BNT111, cemiplimab and both)
- Related TEAEs leading to permanent discontinuation of treatment

Analyses of adverse events

The number and percentage of patients reporting TEAEs will be summarized by PT nested within SOC. If a SOC / PT is reported more than once for a patient, the patient will only be counted once for this SOC / PT. Strongest relationship or worst grade will be counted if a TEAE is reported more than once by the same patient for a SOC / PT.

All AE summary tables will be presented for BNT111 and cemiplimab separately and sorted alphabetically by SOC and PT within SOC.

Analyses of other adverse events (excluding serious AEs)

The number and percentage of patients reporting other TEAEs (excluding TESAEs) will be summarized by PT nested within SOC. If a SOC / PT is reported more than once for a patient, the patient will only be counted once for this SOC / PT.

All AE summary tables will be presented for BNT111 and cemiplimab separately and sorted alphabetically by SOC and PT within SOC.

Treatment-related AEs

The number and percentage of patients reporting treatment-related TEAEs will be summarized by PT nested within SOC for BNT111 and cemiplimab separately and related to both the treatments.

Statistical Analysis Plan (SAP) BNT111-01

Page 48 of 78 Version: Final v7.0 Date: 05Mar2024

In addition, treatment-related for both randomized and add-on treatment TEAEs will be summarized by PT nested within SOC for BNT111 and cemiplimab separately.

AESIs (irAE and Infusion-related AEs)

The number and percentage of patients with AESIs, irAEs grade ≥3 related to cemiplimab and infusion-related reactions grade ≥2 related to cemiplimab will be summarized by PT nested within SOC.

TEAE by NCI-CTCAE grade

The number and percentage of patients with TEAEs will be summarized by worst NCI-CTCAE grade by PT nested within SOC. Worst grade will be counted if a TEAE is reported more than once by the same patient for a SOC / PT.

TEAE by NCI-CTCAE grade by relationship status

The number and percentage of patients with related and not related TEAEs will be summarized by worst NCI-CTCAE grade by PT nested within SOC for BNT111 and cemiplimab separately. Worst grade will be counted if a TEAE is reported more than once by the same patient for a SOC / PT.

Serious Adverse Events

The number and percentage of patients with TESAEs will be summarized by PT nested within SOC.

Related Serious Adverse Events

The number and percentage of patients with related TESAEs (for BNT111 and cemiplimab separately and related to both the treatments) will be summarized by PT nested within SOC.

In addition, treatment-related TESAEs for both randomized and add-on treatment will be summarized by PT nested within SOC for BNT111 and cemiplimab separately.

Related Serious Adverse Events by NCI-CTCAE grade

The number and percentage of patients with related TESAEs (for BNT111 and cemiplimab separately and related to both the treatments) will be summarized by worst NCI-CTCAE grade by PT nested within SOC. Worst grade will be counted if a TEAE is reported more than once by the same patient for a SOC / PT

Deaths

All deaths including those that occurred on-treatment (deaths occurred between first
and last trial treatment intake during the study + 30 days) and post-treatment (deaths
occurred after the last trial treatment intake during the study + 30 days), will be listed.
Post treatment deaths will be flagged. In addition to the summary of on-treatment
deaths and post-treatment deaths, an additional summary of all deaths (on-treatment
+ post-treatment) will be provided along with primary reason for death.

Page 49 of 78 Version: Final v7.0 Date: 05Mar2024

- A separate summary of TESAEs leading to death will be provided by PT nested within SOC.
- A separate summary of related TESAEs leading to death (for BNT111 and cemiplimab separately and related to both the treatments) will be provided by PT nested within SOC.

AE listings

All TEAEs, fatal AEs, SAEs, TEAEs leading to dose reduction and interruption, TEAEs leading to permanent discontinuation of treatment, Infusion-related reactions, irAEs, and TEAEs related to trial procedures will be listed.

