- t After informed consent has been obtained, all AEs will be documented on the eCRF, and all SAEs should be reported to the sponsor within the appropriate time frame. All AEs will be reported until 90 d after the last dose of trial treatment (i.e., SFU2 visit). In addition, the sponsor should be notified (even after SFU2 visit), if the investigator becomes aware of any SAE that is believed to be related to prior exposure to trial treatment or a trial procedure.
- u Patient-reported outcomes/quality of life assessment questionnaires must be completed before any assessments are done or any treatment is given on the dosing day. Patients will provide PRO/QoL assessment during trial visits at baseline (C1D1 prior Treatment), C2D1, C3D1, C4D1, every 9±1 wks for the next 9 mon, and every 12±2 wks thereafter until SFU1.

Clinical Trial Protocol BNT111-01

Page 19 of 133 Version: 7.0 Date: 09 FEB 2023

- Randomization must be done before administration of trial treatment.
- Treatment with BNT111 must be initiated no later than 7 d after confirmed eligibility. After administration of BNT111, an initial observation time of at least 6 h is required (see Section 6.8.4.1).

 Treatment is to be continued up to 24 mon or until confirmed disease progression, patient withdrawal of consent or unacceptable toxicity.
- Treatment with cemiplimab must be initiated no later than 7 d after confirmed eligibility. Cemiplimab will be given according to the valid Prescribing Information in the country. The first administration of cemiplimab will be on Cycle 1 Day 1, followed by every 3 wks (±3 d) thereafter. Cemiplimab will be administered after administration of BNT111 with at least a 30 min interval (if feasible, both trial drugs should be given on the same day, a maximal window of 1 wk between administrations would be allowed). There should be an initial observation time of first administration of cemiplimab. From second administration of cemiplimab, no observation time is stipulated with reference to cemiplimab (local protocol should be followed). Treatment to be continued up to 24 mon or until confirmed disease progression, unacceptable toxicity, or patient withdrawal of consent.

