8.4 Adverse events of special interest

An AESI, serious or non-serious, is one of scientific and medical concern specific to the sponsor's product or program, for which ongoing monitoring and rapid communication by the investigator to the sponsor are appropriate. Such an event might warrant further investigation in order to characterize and understand it. Depending on the nature of the event, rapid communication by the trial sponsor to other parties (e.g., regulators) might also be warranted.

The following AEs should be reported if related to cemiplimab:

- Grade ≥ 2 infusion-related reactions are considered AESIs and must be reported within 24 h of identification by the investigator.
- Grade ≥ 3 irAEs are considered AESIs and should be reported within 24 h of identification by the investigator.

Note: An irAE can occur shortly after the first dose or several months after the last dose of treatment. All AEs of unknown etiology associated with drug exposure should be evaluated to determine possible immune etiology. If an irAE is suspected, efforts should be made to rule out neoplastic, infectious, metabolic, toxin or other etiologic causes prior to labeling an AE as an irAE.

AESI including non-serious AESI should be reported via the SAE Report Form according to the timelines and contact details given in Section 10.3.1.10 of this protocol. For non-serious AESI, the seriousness criterion should not be reported/selected as these non-serious AESIs are to be reported according to the timelines of SAEs, but mostly do not have the seriousness of an SAE.

Page 86 of 133 Version: 7.0 Date: 09 FEB 2023

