10.3.1 Definition of AE

AE definition

An AE is any untoward medical occurrence in a patient or clinical trial patient, administered a pharmaceutical product and which does not necessarily have to have a causal relationship with this treatment.

Note: An AE can therefore be any unfavorable and unintended sign (including an abnormal laboratory finding), symptom, or disease (new or exacerbated) temporally associated with the use of a medicinal product, whether or not considered related to the medicinal product.

Page 103 of 133 Version: 7.0 Date: 09 FEB 2023

A TEAE is defined as any AE with an onset date on or after the first administration of trial treatment (if the AE was absent before the first administration of trial treatment) or worsened after the first administration of trial treatment (if the AE was present before the first administration of trial treatment). AEs with an onset date more than 90 days after the last administration of trial treatment will be considered as treatment-emergent only if assessed as related to IMP by the investigator.

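### SAP 8.5.2 gives two rules for treatment-emergent AEs on randomized treatment, and they disagree on related events starting more than 90 days after the last dose

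*SAP*

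**What the plan says.** Protocol 10.3.1 defines a TEAE by onset or worsening on or after the first dose. An event that starts more than 90 days after the last dose "will be considered as treatment-emergent only if assessed as related to IMP by the investigator".

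SAP 8.5.2 has three definitions:

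- **Randomized treatment, first paragraph.** It repeats the protocol definition. Events starting after day 90 "will be considered as treatment emergent only if assessed as related to trial treatment by the investigator, prior to start of Add-on treatment".
- **Randomized treatment, second paragraph.** "An AE will be considered TE for the randomized treatment if it started within 90 days of last dose of randomized treatment", followed by "or until start of add-on treatment whichever comes first". It says nothing about relatedness.
- **Add-on treatment.** Events starting more than 90 days after the last add-on dose "will be considered as TE only if assessed as related to add-on treatment by the investigator".
- **Randomized and add-on combined.** Events starting after day 90 "will be considered as TE only if assessed as related to randomized/add-on treatment by the investigator".

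The last two definitions have no further sentence that narrows them. SAP 8.5.2 then says that all three kinds of TEAE are summarized for the Safety set and the Add-on Treatment set. SAP Appendix 1, which lists departures from the protocol's planned analyses, does not mention the TEAE definition.

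**The concern.** The second paragraph for randomized treatment ends its window at 90 days with no exception. The first paragraph, the protocol and the other two SAP definitions all keep one. A programmer who takes the second paragraph as the operative window would leave late related events out of the randomized-treatment tables. That would be a departure from the protocol that Appendix 1 does not declare.

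The events at stake are few but not trivial. Protocol 8.4 warns that "An irAE can occur shortly after the first dose or several months after the last dose of treatment". Routine AE collection ends at SFU2, 90 days after the last dose. Beyond that visit, SOA1 footnote t says that "the sponsor should be notified (even after SFU2 visit), if the investigator becomes aware of any SAE that is believed to be related" to trial treatment or a trial procedure. So what reaches the database with an onset after day 90 is mainly related and serious. It is mainly rather than only so, because the SFU2 visit has a window of ±7 days. TEAEs by grade, seriousness and relationship are a secondary safety endpoint.

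**Working it through.** The documents state no figure here, so the check is to apply each rule to the same test records. The inputs are the definition in Protocol 10.3.1, the two paragraphs of SAP 8.5.2 for randomized treatment, and the combined definition in SAP 8.5.2. In every record the AE was absent before the first dose.

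| Test record | Protocol 10.3.1 | SAP first paragraph | SAP second paragraph | SAP combined |
|---|---|---|---|---|
| A. Related, onset 120 days after last randomized dose, no add-on | TEAE | TEAE | outside the window | TEAE |
| B. Unrelated, onset day 120, no add-on | no | no | no | no |
| C. Related, onset day 60, no add-on | TEAE | TEAE | TEAE | TEAE |
| D. Arm 2 or 3, onset after the first add-on dose while treatment continues | TEAE (no split by period) | TEAE as worded | not randomized-period | TEAE |

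**Record A** is where the rules conflict. The affected class is related events that start more than 90 days after the last randomized dose and before any add-on. In practice these are Arm 1 patients and Arm 2 or 3 patients who take no add-on.

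**Consequence for Arm 1.** These patients never receive add-on treatment, so their last randomized dose is also their last dose under the combined definition. Their randomized and combined counts should be equal. Under the second paragraph, record A is missing from the randomized table and present in the combined one.

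**Record D** shows what the second paragraph contributes. In the first paragraph the words about add-on qualify only the clause on events after day 90. The add-on cut-off for all other events stands only in the second paragraph.

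**Does another passage settle it?**

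- SAP 8.1 restricts safety data for the Safety set to the time before the first add-on dose, but it excludes adverse events from that rule.
- Appendix 1 is silent.
- Neither paragraph of 8.5.2 is said to take precedence.
- The first paragraph closes by choosing the earlier of two dates without naming two dates, so it does not resolve the matter either.

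**The case against.** The best defence is that the two paragraphs can be read together. The first is worded as the definition. The second says if, not only if, and looks intended to divide events between the randomized and add-on periods, which would explain why the other two definitions lack such a sentence. This reading is possible and may be what was meant. It does not remove the problem, because the second paragraph sets an end date and is the only sentence that says when an event is TE for the randomized treatment. Either paragraph could reasonably be coded.

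The second defence is that little is lost, and much of this stands. A reader might infer that late related events vanish from the report. They do not:

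- The combined definition keeps them and is summarized for the Safety set, with dedicated combined summaries of related TEAEs and related TESAEs.
- SAEs, fatal AEs and irAEs are listed, and deaths are both listed and summarized.

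A reader might also infer that the AESI tables shrink. The text does not support that. AESIs are defined by grade and relation to cemiplimab, with no treatment-emergence condition. SAP 8.1 mentions a treatment-emergent flag for irAEs with incomplete dates, but no AESI table text applies it.

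Finally, because the second paragraph states no start date, a reader might infer that it admits screening events that never worsen. The definition directly above it supplies the first-dose bound, so that reading is strained and no weight is placed on it.

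**Conclusion.** Wrong as written, with a narrow effect. SAP 8.5.2 gives two rules under one heading that disagree on related AEs starting more than 90 days after the last randomized dose and before any add-on. If the second paragraph is programmed, those events drop out of the randomized-treatment TEAE, related TEAE and TESAE summaries, contrary to Protocol 10.3.1, and Arm 1 counts can differ between the randomized and combined tables.

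The number of events is probably small. The documents give no rate of late related events, so neither a count nor a range can be given. The conclusion assumes only that the second paragraph may be taken as the operative window, which its wording allows. The primary endpoint and its error control are unaffected.

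**What to change.** Replace the second paragraph with: 'For the randomized treatment, an AE is treatment-emergent if it starts or worsens on or after first dose and before first add-on dose, and either within 90 days after last dose of randomized treatment or, later than that, if assessed as related.'

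On the test records this counts A and C and leaves out B and D, which agrees with the protocol and keeps the periods separate.

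Deleting the second paragraph without a replacement would be a mistake. As record D shows, an event arising on add-on treatment in Arm 2 or 3 would then also meet the randomized-treatment definition, and toxicity from the combination period would be credited to monotherapy.

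The cost is one SAP sentence and the matching program logic. No new data are needed. A few late related events may be added to the randomized-treatment tables.
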